NIH	National Institutes of Health
NIH IC	NIH Institute or Center
OHRP	Office for Human Research Protections
PI	Principal Investigator
QA	Quality Assurance
QC	Quality Control
SAE	Serious Adverse Event
SAP	Statistical Analysis Plan
DSMC	Data Safety Monitoring Committee
SoA	Schedule of Activities
SOC	System Organ Class
SOP	Standard Operating Procedure
UADE	Unanticipated Adverse Device Effect
UP	Unanticipated Problem
US	United States

1 STUDY SUMMARY

1.1 Synopsis

Title:	Open label comparison of injectable extended release buprenorphine (CAM2038, Brixadi®) and naltrexone (Vivitrol®) for the treatment of opioid use disorder
Short Title:	Brixadi and Vivitrol
Study Description:	
This study will elucidate the cognitive mechanisms of response to opioid agonists and antagonists used to prevent relapse in OUD through investigation of the underlying neural circuits. We shall use previously validated cognitive probes, functional Magnetic Resonance Imaging (fMRI), and extended-release injectable preparations of opioid partial agonist buprenorphine (XR-BUP, Brixadi) and opioid antagonist naltrexone (XR-NTX, Vivitrol), in OUD patients. Using two medications with opposing mu opioid receptor action will allow a comprehensive evaluation of the mechanisms of response to relapse prevention pharmacotherapy in OUD. The study will determine the presence of treatment effects in the domains of executive function, incentive salience, and resting functional connectivity and the interaction that will indicate a difference between the two medications. Then we will evaluate the ability of the brain fMRI signal to explain relapse defined by % of opioid-positive urine tests and adherence to the study interventions. Participants will be recently detoxified treatment-seeking patients with OUD who will receive 3 monthly injections of XR-NTX or XR-BUP and have weekly urine toxicology monitoring. The project will enroll 200 participants over 6 years. The proposal would be the first neural systems' level investigation of the cognitive effects of the next generation extended release preparation of buprenorphine and naltrexone to explain the individual heterogeneity of OUD treatment response and failure. This project has the potential to advance the theory and personalized treatment of OUD by elucidating the brain mechanisms of vulnerability to relapse in OUD and in SUD in general.
 
The proposal is similar to an existing UPenn IRB protocol 814234 and Biomarkers of disease and response to treatment in opioid addiction in all aspects except the addition of XR-BUP, Brixadi.

Objectives:	Compare brain fMRI response to injectable extended-release buprenorphine (Brixadi, XR-BUP) and naltrexone (XR-NTX, Vivitrol)

**Medications
and
Interventions**

XRBUP (CAM2038, Brixadi) is a subcutaneous (SC) injectable extended-release formulation of buprenorphine that has been developed by Camurus AB (Sweden) and licensed in the US by Braeburn Pharmaceuticals. Brixadi is available in a range of weekly and monthly doses (8,16,24 and 32 mg weekly and 64 and 96 mg monthly) (Lofwall et al 2018). CAM2038 was approved under brand name Buvidal for OUD by the European Medicines Agency and approved as Brixadi by the FDA. This creates a unique window of opportunity for research. Braeburn, the US licensee of Brixadi has agreed to provide the study medication at no cost (See Letter of support).

XRNTX (Vivitrol): is a monthly extended-release intramuscular injection of 380 mg of naltrexone manufactured by Alkermes Inc, that has been approved by the FDA for OUD since 2010 (Lee et al 2017) XRNTX maintains therapeutic levels of naltrexone and its active metabolites for approximately 4 weeks after each injection.

Functional magnetic resonance imaging (fMRI): is an established method of clinical medical imaging. Combined with **neurocognitive testing**, standard clinical MRI scanner can be used as an accurate and robust means of evaluation of brain response to medications such as opioid agonists and antagonists, that modulate cognitive and motivational processes in addiction (Davis et al 2017, Moningka et al 2019).

Neurocognitive testing: Psychological tasks are a well-established means to evaluate a particular cognitive or emotional domain. We shall use established tasks probing four domains: motivation, response inhibition, emotional controls and awake rest during the fMRI sessions, to simultaneously assess domain-specific behavioral performance and brain activity.

Group (XRNTX, XRBUP) by Session (PRE, ON) **interaction** in the brain fMRI signal in 4 cognitive domains

**Primary
Endpoint:**

Domain-specific cognitive performance, Urine toxicology, Adherence to follow up and treatment visits.

**Secondary
Endpoints:**

**Study
Population:**

200 individuals between the ages of 18 and 65 who have a diagnosis of Opioid Use Disorder (OUD).

Phase:

Phase 2a/b

**Description of
Sites/Facilities**

UPenn Department of Psychiatry, Center for the Study of Addictions, [name]

**Enrolling
Participants:**

UPenn Center for the Study of Addictions

Description of Study Intervention: XRBUP (CAM2038) or XRNTX (Vivitrol)

Study Duration: Six years (72 months)

Participant Duration: 20 weeks

2 INTRODUCTION AND RATIONALE

This document is a protocol for a human research study. This study is to be conducted according to US and international standards of Good Clinical Practice (FDA Title 21 part 312 and International Conference on Harmonization guidelines), applicable government regulations and Institutional research policies and procedures. This proposal brings four main innovations: It would be the first neural systems' level investigation of the cognitive effects of extended-release preparations of a partial opioid agonist (XRBUP) and an antagonist (XRNTX). These formulations remove the pharmacokinetic and motivational imbalance between the monthly injectable naltrexone and daily sublingual buprenorphine that were compared in prior research (Wang et al 2015). In addition to differences in pharmacokinetics, long acting formulations are likely to have a different effect on patients' expectations of possible reward, which directly impacts dopaminergic signaling that regulates salience of drug and non-drug stimuli. Second, it would be one of the first comprehensive investigations of the cognitive effects of buprenorphine in OUD. Third, it would apply machine-learning algorithms to the integrated brain-behavior models to explain the individual heterogeneity of treatment response to MAT. Last, this would be the 1st study of the next generation injectable buprenorphine (Brixadi) that is expected to appear on the US market by September 2023 but is already approved by the FDA in terms of safety and efficacy. The significance of this project is in its potential to advance OUD theory and treatment by elucidating the brain mechanisms of vulnerability to relapse. Further, the results of this study could lay the foundation for improving treatment outcomes in OUD and in SUD in general. Project goals also directly address national public health priorities recently outlined by the directors of NIDA and the NIH: finding novel and increasing the effectiveness of available OUD treatment strategies (Volkow et al 2017).

2.1 Study Rationale

Investigation of brain and behavioral mechanisms of the effects of the two injectable extended release preparations for the treatment of opioid use disorder with the ultimate goal of improving treatment outcomes in opioid use disorder. Both of these preparations are FDA-approved. One is opioid antagonist (Vivitrol, XRNTX), and other is a partial opioid agonist (Brixadi, XRBUP).

2.2 Background

Opioid use disorder (OUD) has reached epidemic proportions in the US, with devastating public health consequences (Compton et al 2016, Hedegaard et al 2017, Jiang et al 2017). Since 1999, the number of deaths due to opioid overdose has more than quadrupled (Jones 2013), and it is now among the leading causes of death in adolescents and young adults (Jones et al 2015). Treatment of OUD has three distinct targets: (i) prevention of opioid overdose in users of illicit drugs, (ii) detoxification from physiological dependence, and (iii) prevention of relapse. Of these, relapse presents the greatest treatment challenge because it persists after protracted abstinence and even a brief relapse can be fatal. There are two efficacious classes of medication-assisted therapies (MAT) for OUD: opioid agonists (e.g. methadone and

buprenorphine) and antagonists (e.g. naltrexone). Both have high affinity for the mu-opioid receptor (MOR) with antagonists lacking inherent opioid-like activity. Both MAT agonists and antagonists are well tolerated and highly effective at preventing relapse and withdrawal when taken (Lee et al 2017, Tanum et al 2017, Latif et al 2018). Nevertheless, in the clinic, MAT is associated with significant rates of continued illicit use that is on a continuum with non-adherence to MAT and relapse (Soyka et al 2008, Tkacz et al 2012, Hser et al 2014, Schuman-Olivier et al 2014). Vulnerability to relapse is a multidimensional phenotype comprised of pre-treatment characteristics and treatment response. Understanding the individual variability in treatment response is critical for elucidating the mechanisms of relapse. Although motivational and cognitive factors are ultimately responsible for relapse, cognitive assessments have not provided robust explanation of MAT effects (Nunes et al 2015). fMRI allows probing the cognitive mechanisms of MAT by studying the underlying neural circuitry. Studies indicate that incentive salience and executive functioning are key cognitive-behavioral domains that exhibit abnormalities in established OUD (Kwako et al 2016). Our preliminary studies have identified probes of executive function and incentive salience with well-established normative brain fMRI signatures that are sensitive to oral methadone or extended-release naltrexone (XRNTX) (Langleben et al 2014, Wang et al 2015, Shi et al 2018, Wang et al 2018). Comparable data on sublingual (transmucosal) buprenorphine/naloxone (Suboxone) is extremely limited and is lacking entirely on the recently approved extended-release injectable buprenorphine (XR-BUP) preparations (Becerra et al 2013, Pujol et al 2018). Comparisons between buprenorphine and naltrexone introduced by the differences in routes of administration (Lee et al 2017, Tanum et al 2017).

2.2.1 *Pharmacokinetics, Pharmacodynamics and Toxicology*

For the present proposal, we will use injectable extended release naltrexone Vivitrol (XRNTX) that has been FDA approved since 2010 for the treatment of OUD and CAM2038 or Bixadi, manufactured by Camurus AB (Sweden) and Braeburn Pharmaceuticals (USA) (Lofwall et al 2018). XRNTX is a monthly IM injection of naltrexone. XR-BUP is a weekly or monthly injection of buprenorphine. The active ingredients of Vivitrol and Bixadi are naltrexone and buprenorphine, both of which have been in clinical FDA-approved use for over 30 years. Bixadi and Vivitrol are injectable extended release preparations of these two well known drugs.

Complete PK, PD and Toxicology profile for Vivitrol is available from attached [package insert](#) and at <https://www.vivitrol.com/>. Complete PK, PD and Toxicology profile for Bixadi is available from Braeburn Website:

<https://braeburnrx.com/braeburns-bixadi-buprenorphine-extended-release-subcutaneous-injection-ciii-receives-fda-approval-for-moderate-to-severe-opioid-use-disorder/>

Opioid receptor actions of buprenorphine include analgesia, alleviation of withdrawal-like symptoms, and antidepressant effects. Opioid receptor actions of naltrexone include opioid receptor blockade. The main potential side effect of both medications is precipitated opioid withdrawal when administered to an individual who has not been sufficiently detoxified from opioids. Buprenorphine may rarely lead to over-sedation and respiratory depression in overdose, although because of its mixed agonist/antagonist properties, it is very unlikely. Other important side effects of naltrexone include prevention of action of opioid analgesics and hepatotoxicity when given to patients with compromised liver function. This is avoided by testing liver function prior to and during treatment.

Urine drug screen (UDS) and self-report of past use have long been the two main outcomes variables in SUD treatment studies. XRNTX and XRBUP differ from the traditional pharmacotherapies because once administered, the patient cannot terminate their effect for approximately one month (Dunbar et al 2007). During this time, continued illicit opioid use has more psychological than pharmacological significance (Sullivan et al 2013). Moreover, receiving an injection is 100% verifiable and not subject to interpretation. Thus, adherence is an additional valid measure of treatment response to injectable extended-release medications. Concurrent use of non-opioid medications, which XR MAT does not prevent, has been shown to be associated with unfavorable outcomes (Grella et al 2011, Wang et al 2015). This justifies its inclusion as an exploratory outcome variable in the clinical-behavioral model.

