XRNTX (Vivitrol) is an FDA-approved medication for opioid relapse prevention (<https://www.vivitrol.com/content/pdfs/prescribing-information.pdf>.) It is a suspension of 380 mg of naltrexone in a nanoparticle slow release vehicle, for intramuscular injection. The most important and nevertheless rare side effects are (1) precipitated opioid withdrawal; (2) anxiety; (3) pain and infection at the injection side, (4) liver toxicity in cases of compromised liver function and (5) loss of opioid tolerance and therefore greater risk of opioid overdose after study completion or in case of drop out. These will be minimized by the following measures:

Ensuring that the participant is not physiologically opioid dependent, by obtaining an opioid-negative urine test, self-report of no opioid use in the last 5 days (7 days for buprenorphine and methadone) and a negative naloxone challenge test (Langleben et al *Addiction Biology* 2014).

Anxiety is usually self-limited and will be treated symptomatically, initially with the weekly psychotherapy and if necessary, with medications indicated for this purpose.

Meticulous injection technique: our experienced personnel who has administered thousands of Vivitrol injections without ANY complications over a decade, psychoeducation

Applying the exclusion criterion regarding elevated liver function tests labs described in the Exclusion Criteria section above.

Risks of the study unrelated to the investigational product:

- 1) Exposure to high magnetic fields: The Siemens Magnetom Prisma 3 Tesla MRI scanner we will use in the study is a clinical MRI system approved by the FDA. Information about this scanner is available on manufacturers website: <https://www.siemens-healthineers.com/en-us/magnetic-resonance-imaging/3t-mri-scanner/magnetom-prisma>
- 2) FDA guidelines and the IRB committees consider this scanner to be a minimal risk device. Specific Absorption Rates (SAR) of electromagnetic energy by the body is controlled by a directional coupler that serves as a circuit breaker that switches the magnet off, if the local SAR exceeds the FDA limit of 8 watt/kg in any gram of tissue. The exposure characteristics are kept on file with a copy of the consent form at the University of Pennsylvania Center for MRI and Spectroscopy (CAMRIS). Although pregnancy is not a contraindication for MRI, pregnant women will not be eligible for XRNTX and therefore, screened out prior to them being considered for our study.

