5.2 Exclusion Criteria

1. Psychiatric Co-morbidities:
 - a) Lifetime diagnoses of any psychotic disorder, e.g. schizophrenia, schizoaffective disorder, bipolar affective disorder type 1.
 - b) Psychiatric co-morbidities: Psychiatric disorders requiring current medication treatment, e.g. moderate to severe depression. Mild to moderate Depressive and Anxiety disorders and Attention Deficit Hyperactivity Disorder that do not require prescription stimulants and DSM Cluster B and C personality disorders are also allowed.
 - c) Polysubstance users whose drug of choice is not an opioid.
2. Contraindications for XRNTX or XRBUP e.g. active liver disease.
8. Medical and surgical conditions such as malignancy that may affect patients' ability to receive XRNTX or XRBUP treatment because it may interfere with opioid analgesia
9. Contraindications for MRI, e.g. claustrophobia, indwelling foreign magnetic agents.

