Participants who pass Screening will be invited to attend Intake session at UPenn Center for Studies of Addiction ([name]). An IRB (UPENN) approved Informed Consent will be read verbatim by a trained research staff. At the end of the consent session, a quiz is given. Subjects scoring below 100% correct will receive additional instruction regarding the study and consent form. Incorrect questions from the quiz will be administered again until all questions are answered correctly. All participant questions will be answered as appropriate after which the Informed Consent will be completed (signed and dated).

After signing the consent, participants would also be asked to grant access to their medical records at University of Pennsylvania and other institutions to share their health information that may include diagnoses, medications, hospital admissions, laboratory and imaging studies and participation in treatment programs including substance use disorder. This will be done by signing a **“RESEARCH PARTICIPANT AUTHORIZATION TO OBTAIN AND REVIEW HIPAA-**

PROTECTED MEDICAL RECORDS AND COMMUNICATION WITH THEIR HEALTH CARE PROVIDERS”

Participants' eligibility for fMRI and XRNTX and XRBUP will be determined by history and physical examination and laboratory testing, e.g. Blood chemistry including Liver Functions and Complete Blood Count (CBC) (Cornish et al 1997). Additional tests relevant to the specific detoxification setting, such as 12 lead Electrocardiogram (ECG), Xray will be performed if clinically indicated.

Intake Procedures at Treatment Facilities:

Participants found to be eligible at screening who are unable to attend intake at our center because they are currently inpatient, will undergo intake procedures at their inpatient treatment facility. Private space for the intake sessions will be secured in coordination with inpatient clinical staff.

The following procedures will be done at the inpatient facilities to reduce the delay in enrolling eligible participants.

- Informed consent, informed consent quiz and HIPAA authorization form administered by the trained study member.

Non-invasive assessments and measures will be administered by the trained study members using portable tablets.

Opioid withdrawal management (detoxification) and induction to monthly MAT injections:

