Short Form-McGill Pain Questionnaire-2 (SF-MPQ-2) (Dworkin et al 2015) (PhenX #190901) is a 22-item self-administered questionnaire that asks about the different qualities of pain and related symptoms. Respondents are asked to rate the intensity of each type of pain they felt during the past week on a scale from 0 to 10

Timeline Follow-Back Interview (TLFB) (Sobell et al 1992). The TLFB is a 15-30-minute, semi-structured interview designed to measure self-reported drug use. It will be used at baseline to capture all drug use in the past 30 days including prescribed concomitant medications (PhenX 27016266).

Weekly online self-reported TLFB is a modified TLFB interview that uses a calendar-based format to record participants' self-report of past week drug use.

Urine Toxicology: is a standard procedure using commercial clinically approved kits that will be administered by trained staff member.

8.2 Safety and Other Assessments:

the following assessments will serve as safety measures when their results indicate change from baseline indicative of AE or baseline reading indicating that a participant meets an exclusion criterion.

Screening & Intake ([Appendix Section 12.1](#)): Candidates will be screened by phone or in person at a referral site by a trained staff member(research assistant, coordinator, RN, psychologist or physician). History and physical as well as basic chemistry and blood count will be done at Intake. [see section 6.1 above].

Opioid withdrawal management (detoxification) and induction to monthly MAT injections

will be performed by the study physicians. The 1st monthly injection will be administered by an experienced nurse practitioner after induction (7-14days) is complete.

Neuroimaging (MRI): The MRI session will take place after detoxification and immediately before MAT induction ([Appendix Section 12.1](#)) by a trained and authorized technician.

MINI International Neuropsychiatric Interview (MINI) (Sheehan DV, 1998; 59(suppl 20)). The MINI is a clinician administered neuropsychiatric interview for symptoms across 17 of the most common mental health disorders. The DSM-5 version of the MINI will be administered.

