Missing Data and Nonadherence: For the longitudinal analyses described above, premature discontinuation from treatment and occasional missing daily use indicators will lead to incomplete data. The mixed effects models described above can make use of all available data provided by subjects, but the inferences drawn from them will be unaffected by the missing data only if the missing data can be regarded as ignorable, in the sense of Laird ⁵⁵. To assess the sensitivity of our analyses to this assumption, we will use shared parameter models, which allow for correlated random effects underlying the cocaine use measurements and the pattern of dropout ⁵⁶. We will also use selection models to examine the effects of missing data ^{57,58}. We will explicitly model the probability of premature discontinuation at a time point as a function of baseline characteristics and responses at previous time points, using a logistic regression model, and incorporate the predicted probabilities into a weighted analysis of the main hypotheses. We will do analyses in a range of assumptions and assess the sensitivity of results to them ⁵⁸. We will use urine drug screens, record of clinic visits and receipt of injectable medications as measures of compliance with assigned medication regime. We will use the methods of Nagelkerke et al ⁵⁹ and Small et al ⁶⁰, to obtain estimates of the intervention effect in a population compliant with treatment i.e. the Complier Average Causal Effect (CACE).

Safety: The adverse event responses will be analyzed as a measure of safety. Total number of adverse events, adverse events leading to discontinuation (in the judgment of the study physician), % of patients reporting at least one adverse event, clinical lab assessments, vital signs and

evidence of clinical worsening (by urine drug screen results and TLFB results) will be considered in assessment of safety. In a manner parallel to the analysis for therapeutic response, medication group, gender, age and other clinical variables will be entered into a generalized linear mixed effects model to predict adverse events.

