13 APPENDIX

13.1 Schedule of Activities (SoA)

	Screening detox and randomization (Day -14)	MRI Scan 1 Baseline (day 0)	Induction to XRBUP or XRNTX (day 0-10)	Injection 1 (day 10) + weekly follow up	Injection 2 (day 40)	MRI Scan 2 On Treatment (day 55)	Injection 3 (Day 70)	Weekly Follow- up End of study and referral (Day 100)
Psychiatric and medical								
Demographics (age ¹ , sex ¹ , edu ¹)		X						
History, physical and labs (C.4.a)		X						
SILS		X						
MINI (EOS* – end of study)		X						X EOS*
Addiction Severity Index ¹		X						X EOS*
Clinical/Behavioral (C.3.a)								
HAM-D ² , HAM-A ² , COWS ²	X	X	X		X	X		X
SOWS, Opioid Craving Scale ² , SF-MPQ-2 ² , STAI-6		X	X	X	X	X		X
TLFB interview	X	X	X		X	X		X
Ten-drug urine drug screen (UDS)	X	X	X	X	X	X		X
Go-NoGo errors of commission ²		X		X				
Neuroimaging (Section C.3.b)								
Go-NoGo fMRI ³		X			X			
Opioid Cue task fMRI ³		X			X			
Resting-state fMRI ³		X			X			
MPRAGE (anatomical MRI scan)		X			X			

PRINCIPAL INVESTIGATOR SIGNATURE

STUDY SPONSOR: [name]

STUDY TITLE: **Open label comparison of injectable extended release preparations of buprenorphine (Brixadi®) and naltrexone (Vivitrol®) for the treatment of opioid use disorder**

STUDY ID 843403

PROTOCOL VERSION V5.0

I have read the referenced protocol. I agree to conduct the study in accordance to this protocol, in compliance with the Declaration of Helsinki, Good Clinical Practices (GCP), and all applicable regulatory requirements and guidelines.

Principal Investigator Name	[name]	Signature
Affiliation:	University of Pennsylvania	Date 7/17/2023

END OF DOCUMENT

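### Section 2.2.1 relies on liver testing during treatment, but the documents schedule labs only once, before treatment, and schedule no vital signs

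*Combined protocol and SAP*

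**What the plan says.** Section 2.2.1 names hepatotoxicity in patients with compromised liver function as an important side effect of naltrexone and says of it: "This is avoided by testing liver function prior to and during treatment". Section 2.3.1 lists liver toxicity among the important though rare risks of both study drugs. For each drug it gives this mitigation: "Applying the exclusion criterion regarding elevated liver function tests labs described in the Exclusion Criteria section above".

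The exclusion list in Section 5.2 has one entry on the liver: "Contraindications for XRNTX or XRBUP e.g. active liver disease".

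On timing, the Intake part of Section 6.1 names "Blood chemistry including Liver Functions and Complete Blood Count (CBC") among the tests that determine eligibility. Section 8.2 says: "History and physical as well as basic chemistry and blood count will be done at Intake". In the Schedule of Activities (Section 13.1) the row "History, physical and labs (C.4.a") carries one mark, which in the text as supplied falls under "MRI Scan 1 Baseline (day 0").

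The safety paragraph of Section 9.4.1 includes "clinical lab assessments, vital signs and" evidence of clinical worsening among the things to be considered in assessing safety.

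**The concern.** Section 2.2.1 offers on-treatment liver testing as the reason a named risk is acceptable. A site that follows the schedule exactly would not do that testing. The point matters more for depot drugs, because the background section itself notes that a patient cannot end the effect of an injection for about a month.

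There is also a consequence for the safety assessment. Section 8.2 describes its measures as working through change from baseline, or through a baseline reading that meets an exclusion criterion. Change from baseline needs a later value. With one pre-treatment lab value and no scheduled vital signs, the lab and vital-sign inputs in 9.4.1 have no systematic post-baseline content. A report with no hepatic signal could then mean that there was none, or that nobody tested.

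The entry safeguard has a related gap: 2.3.1 points to a criterion on elevated liver tests that a reader of 5.2 will not find.

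**Working it through.** The documents give no statistical figure to reproduce. The check is a count from the schedule, set against every section that mentions labs, liver function or vital signs.

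**Count from Section 13.1.** The schedule has 8 columns: screening (day -14), baseline scan (day 0), induction (days 0-10), injection 1 (day 10), injection 2 (day 40), second scan (day 55), injection 3 (day 70) and end of study (day 100).

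- Columns after baseline: 8 − 2 = 6.
- Marks in the labs row: 1, at baseline. Marks after baseline: 0 of 6.
- Rows for vital signs: 0, so 0 of 8 columns.

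**Does the count depend on how the table was extracted?** Column positions are not fully reliable. The second set of imaging marks falls under injection 2 (day 40) rather than under the second scan (day 55). But the labs row has one mark wherever it sits, and Sections 6.1 and 8.2 independently put chemistry at intake. The conclusion needs only those two facts.

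**Sections side by side.**

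| Section | What it provides | Scheduled liver test after baseline? |
|---|---|---|
| 2.2.1 | Says testing happens before and during treatment | Asserted, no visit named |
| 2.3.1 | Liver risk handled through an entry criterion | No |
| 6.1 | Liver functions as part of eligibility | No |
| 7.2 | A lab abnormality may be a reason for withdrawal | No |
| 8.2 | Chemistry and blood count at intake | No |
| 8.3.4 | On-study safety by history, examination and instruments | No |
| 8.3.7 | Pregnancy test before scans | No |
| 9.4.1 | Labs and vital signs considered for safety | No |
| 13.1 | One mark in the labs row | No |

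The only laboratory tests placed on study after baseline are urine drug screens and the pregnancy test before scans. Vital signs are mentioned only in 9.4.1.

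**Length of the untested period.** With the three injections in 13.1, from day 10 to day 100 is 100 − 10 = 90 days. Section 4.1 speaks of two monthly injections, and Section 6.4 lists days 10 and 40 only. On that reading, with the schedule's own spacing of 40 − 10 = 30 days, cover runs to about day 40 + 30 = 70, that is 70 − 10 = 60 days. The range is therefore about 60 to 90 days. It starts earlier for XRBUP, because Section 6.1 gives weekly depot injections during induction. The number of scheduled liver tests in the period is 0 on either reading.

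**Entry criterion.** Section 2.3.1 refers to a criterion on elevated liver function tests. Section 5.2 names active liver disease as an example of a contraindication and mentions no liver test and no level.

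**The case against.** The best case on the other side is that nothing in the documents forbids liver tests on treatment. Section 8.3.5 requires weekly questioning about adverse events, with examination as appropriate. Section 8.3.4 includes physical examination, which may well include vital signs. Section 8.3.1 treats clinically significant abnormal results as adverse events. The oversight section also refers to a separate monitoring plan, and the labs row cites a section C.4.a. Neither was available for this review, and either might contain more. The risk is described as rare and tied to compromised liver function, and that group is screened at entry.

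Most of this stands as a limit on the point rather than an answer to it. Four stronger readings are tempting, and the documents do not support them:

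- **That on-treatment monitoring cannot happen, or that the trial never looks.** Tests prompted by an adverse event remain open. What is missing is systematic testing.
- **That lab results may arrive after the first dose,** because the mark sits at day 0 and induction follows the scan. This rests on one column position in an unreliable table. Sections 6.1 and 8.2 put chemistry at intake, for eligibility.
- **That a planned comparison of labs between arms is lost.** Section 9.4.1 says that labs and vital signs will be considered. The only safety model it describes predicts adverse events.
- **That the liver safeguard at entry fails outright.** Section 6.1 bases eligibility on liver functions, and 5.2 excludes active liver disease. What is missing is the specific criterion that 2.3.1 says is there.

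Tests prompted by events do not replace scheduled ones. They miss changes without symptoms, and in a trial described as open label the decision to test can depend on the arm.

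**Conclusion.** The inconsistency is real. On the documents in hand, Section 2.2.1 claims liver testing during treatment that neither the schedule nor the procedure text contains. Scheduled liver tests after baseline number zero in 6 columns, over roughly 60 to 90 days of monthly depot treatment. Vital signs are scheduled nowhere. The lab and vital-sign inputs to the safety assessment would therefore lack systematic post-baseline values. The liver exclusion cited in 2.3.1 does not appear in 5.2.

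This rests on two assumptions: that the single mark in the labs row is complete, which the intake timing in 6.1 and 8.2 supports, and that no document outside those supplied adds on-treatment labs.

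The finding is a count per participant and does not depend on the number treated. A reader might infer 100 exposed participants per arm from the 200 in the synopsis. The documents do not support that: 200 is the recruitment target, randomization follows detoxification, no allocation ratio is stated, and Section 9.2 works with 80 per group. The fMRI endpoints are unaffected. The matter concerns a stated participant safeguard and how far the safety results can be interpreted.

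**What to change.** The sponsor should reconcile Sections 2.2.1, 2.3.1, 5.2, 8.2, 9.4.1 and 13.1 in one amendment:

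- Either Sections 8.2 and 13.1 carry the on-treatment liver testing that 2.2.1 claims and the vital signs that 9.4.1 uses, or the claim in 2.2.1 and the lab and vital-sign inputs in 9.4.1 are withdrawn.
- Sections 2.3.1 and 5.2 state the same liver exclusion.
- If a separate monitoring plan already contains this testing, the protocol should say so, and the schedule should agree with it.

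Timing, thresholds and action levels are for the sponsor to set; this review proposes none. The cost is the amendment and, if the testing is kept, routine blood draws that the protocol already tells its readers will be done.
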